5.3.2 Dose Adjustments/Modifications/Delays

If the GFR falls below 60 mL/min/1.73m² or 30% lower than baseline then we will suspend treatment until GFR returns to baseline, in consultation with the safety monitoring committee.

For other toxicities thought to be the result of the study drug, including gastrointestinal symptoms, treatment will be suspended until the symptoms resolve. The investigator and patient will consider re-initiation on the basis of clinical findings and symptom severity.

5.3.3 **Duration of Therapy**

Subjects will take the study drug for 28 days at the clinically effective tolerated dosage (Target Dosage). However, if study drug is tolerated and the patient has clinical efficacy at two weeks, the extension phase of the protocol will be offered, in which the patient can continue the study drug for up to 60 months.

5.3.4 Tracking of Dose

Study drug bottles will be returned to assess adherence. Patient medication logs will also be used to aid with adherence.

5.3.5 Limitations on PriorTherapy

Subjects may continue other pre-existing chronic (> 2 weeks) antimicrobial therapies including azole antifungals. Intravenous amphotericin products will be

stopped at least 1 week before initiation of the study drug, and non-intravenous amphotericin products (such as oral AMB swishes) will be stopped at least 72 hours before initiation of the study. Other antimicrobial agents that are added during the course of the study need to be approved by one of the investigators.

5.4 Study Product Accountability Procedures

The dispensing pharmacy will acknowledge receipt of all shipments of investigational drug product and maintain accurate accountability records. The study drug administered to the subject will be documented in the medical record. All study drug will be stored and disposed of according to the manufacturer's recommendations. At each monitoring visit and the conclusion of the study, an inventory of study drug will be performed by the Study Monitor (or designee) and the Investigator (or designee). Any missing supplies must be indicated on the drug accountability form along with an explanation of the discrepancy. The Investigator will be instructed to return all unused study drug to Aquarius or designee, and return a copy of the Clinical Supplies Return Form.

5.5 Concomitant Medications and Procedures

Medications to be reported in Clinical Research Information Management System of the NIAID (CRIMSON) are concomitant prescription medications, over-the-counter medications, and non-prescription medications taken at the time of AEs (all grades).

5.6 **Drug Interactions**

CAMB should be used with caution in patients receiving chemotherapy with certain agents, in patients receiving lymphocyte transfusions, or curare-class paralytic agents. Concurrent use of CAMB with drugs that lower serum potassium requires monitoring of serum potassium levels. Other drugs that have increased risk in the presence of hypokalemia should be used with caution, including digitalis and neuromuscular blockade agents (paralytics). The following drugs are known to interact with AMB and may interact with CAMB:

Antineoplastic Agents

Concurrent use of antineoplastic agents may enhance the potential for renal toxicity, bronchospasm, and hypotension. Antineoplastic agents should be given

concomitantly with caution.

Corticosteroids and Corticotropin

Concurrent use of corticosteroids and corticotropin may potentiate hypokalemia, which could predispose the patient to cardiac dysfunction. If used concomitantly with CAMB, then serum electrolytes and cardiac function should be closely monitored.

Digitalis Glycosides

Concurrent use may induce hypokalemia and may potentiate digitalis toxicity. When administered concomitantly, serum potassium levels should be closely monitored.

Flucytosine

Concurrent use of flucytosine may increase the toxicity of flucytosine by possibly increasing its cellular uptake and/or impairing its renal excretion.

Azoles

In vitro and in vivo animal studies of the combination of AMB and imidazoles suggest that imidazoles may induce fungal resistance to AMB. Combination therapy should be administered with caution, especially in immunocompromised patients.

Leukocyte Transfusions

Acute pulmonary toxicity has been reported in patients simultaneously receiving intravenous AMB and leukocyte transfusions.

Other Nephrotoxic Medications

Concurrent use of AMB and other nephrotoxic medications may enhance the potential for drug-induced renal toxicity. Intensive monitoring of renal function is recommended in patients requiring any combination of nephrotoxic medications.

AMB-induced hypokalemia may enhance the curariform effect of skeletal muscle relaxants (eg, tubocurarine) due to hypokalemia. When administered concomitantly, serum potassium levels should be closely monitored.

5.7 Prohibited Medications and Procedures

Concomitant treatment with all AMB products including liposomal formulations and oral AMB will not be permitted.

Azole antifungals will be permitted if used for another indication besides treatment of Candida infection, such as for the treatment or prevention of mold infection.

6 Study Schedule

See Appendix B for tabulated schedule of procedures and evaluations. See Appendix C for volumes of blood to be collected at each visit. Study visits will take place at the NIH Clinical Center, with the exception of certain sample collections that may be done at a local laboratory as indicated below. Patients may be admitted to the Clinical Center as inpatients on the days that 24-hour PK samples are collected.

6.1 Screening

Enrolled patients will be followed on one of the NIAID protocols that allows treatment and evaluation of underlying immune defects, including protocols #00-I-0159, 93-I-0119, 07-I-0033, 11-I-0187, and 01-I-0202. The eligibility criteria, including medical history and physical examination findings, will be evaluated from the immunologic, genetic, and/or initial infection work up conducted as part of the referring protocol. Laboratory, history, and exam findings to fulfill inclusion and exclusion criteria must be collected within 2 weeks prior to enrollment in this protocol (See Appendix B Schedule of Procedures/Evaluations). If findings are not available from the referring protocol within that timeframe, then physical exam, medical history, blood and urine collection, pregnancy test, and microbiology will be conducted under this protocol. Patients with signs and symptoms of esophageal candidiasis will have an upper endoscopy performed under this protocol within 4 weeks before study drug initiation to document the extent of disease and to allow for biopsy and/or visualizing with culture swabs. Patients will sign an informed consent document before undergoing any research procedures under this protocol.

6.2 Baseline

On Study Day 0, patients will undergo the following procedures:

- Medical/Medication history
- Baseline clinical assessment of Candida infection

- Physical exam
- Blood draw and urine collection (see section 7.4) if screening was more than 72 hours prior
- Microbiology (fungal culture of affected site of Candida infection, see section 7.3), with the exception of esophageal cultures
- Optional collection of peripheral blood mononuclear cells (PBMCs) for storage
- · Optional vaginal secretions collection

If the screening evaluations were conducted with 72 hours of the baseline visit, then blood draw, urine, and vaginal swab collection will not be repeated at baseline.

6.3 Treatment at 200 mg/day

On Study Day 1, patients will undergo clinical assessment and physical exam, and assessment of AEs and concomitant medications. Blood and urine will also be collected for additional laboratory evaluations (see Section 7.4). Patients who are capable of becoming pregnant will have a pregnancy test. Predose blood and saliva PK samples will be collected. Patients will then receive a single 100-mg dose of CAMB, followed by 24-hour PK sampling of blood., urine, saliva, stool (optional), and vaginal secretions (optional).

On Study Day 2, the 24-hour timepoint samples of blood, urine, saliva, stool (optional), and vaginal secretions (optional) will be collected. Patients will undergo assessment of AEs and concomitant medications. Blood will also be collected for additional laboratory evaluations. Patients will then begin 100-mg BID dosing for 14 days. Urinalysis for laboratory evaluation will be collected after the 24-hour urine PK concludes and can be collected after administering the morning dose of study drug.

On Study Day 4 (± 1 day), the following procedures and evaluations will be performed:

- Clinical assessment and physical exam as needed to evaluate new symptoms/complaints
- Assessment of AEs and concomitant medications
- Blood draw and urine collection

On Study Day 7 (\pm 1 day), the following procedures/evaluations will be performed:

- Assessment of AEs and concomitant medications
- · Blood draw and urine collection

For this time point, the patient and the investigator have the option of doing a phone interview and obtaining the blood and urine lab work at a local laboratory. A copy of the results should be sent to the investigator.

On Study Day 14 (± 3 days), before administration of the morning dose, patients will undergo clinical assessment and physical exam with clinical response calculation, and assessment of AEs and concomitant medications. Patients who are capable of becoming pregnant will have a pregnancy test. If the patient is a Clinical Responder and the drug is well tolerated, then the dosage of 100 mg BID will be extended for 14 more days. The patient will only receive the morning dose on Day 14 and the following procedures/evaluations will be performed:

- Blood draw and urine collection
- Collection of 24-hour PK samples: Predose (0-hour timepoint) blood and saliva will be collected, followed by 24-hour PK sampling of blood., urine, saliva, stool (optional), and vaginal secretions (optional)
- Plasma, urine, stool (optional), salivary, and vaginal secretions (optional)
 24-hour timepoint to be collected on Day 15.
- Microbiology (fungal culture of affected site)
- Optional collection of PBMCs for storage

On Study Day 21 (± 3 days), the following procedures/evaluations will be performed:

- Assessment of AEs and concomitant medications
- Blood draw and urine collection

For this time point, the patient and the investigator have the option of doing a phone interview and obtaining the blood and urine lab work at a local laboratory. A copy of the results should be sent to the investigator.

On Study Day 28 (± 3 days), the following procedures/evaluations will be performed:

Clinical assessment and physical exam

- Endoscopy with biopsies for EC patients (within 4 weeks of clinical improvement)
- Assessment of AEs and concomitant medications
- Blood draw and urine collection
- Pregnancy testing
- Trough plasma PK collection
- Microbiology (fungal culture of affected sites)
- Optional collection of PBMCs for storage

Study Day 42 (± 3 days) will be the post-treatment End of Study visit for patients who continued 200 mg/day. For this visit, the patient and the investigator have the option of doing the assessment over the telephone instead of making a clinical visit. In this instance the laboratory testing should be performed by a local laboratory and a copy of the results should be sent to the investigator. The following procedures/evaluations will be performed:

- Assessment of AEs
- Blood draw and urine collection

6.4 Dose Escalation to 400 mg/day

If on Day 14 the patient is determined to not be a Clinical Responder but the study drug is well tolerated, then the dosage will be increased to 400 mg/day. These patients will receive only the morning dose (200 mg) on Day 14. The following procedures will be performed:

- Blood draw and urine collection
- Pregnancy testing (result confirmed before administration of dose)
- Collection of 24-hour PK samples: Predose (0-hour timepoint) blood and saliva will be collected, followed by 24-hour PK sampling of blood., urine, saliva, stool (optional), and vaginal secretions (optional)
- Plasma, urine, stool (optional), salivary, and vaginal secretions (optional)
 24-hour timepoint to be collected on Day 15
- Microbiology (fungal culture of affected site)
- Optional collection of PBMCs for storage

Starting on Day 15, patients will be dosed with 400 mg/day (200 mg BID) for 14 days. Prior to dosing, patients will undergo assessment of AEs and concomitant medications. Blood will also be collected for additional laboratory evaluations. Patients will then begin 200-mg BID dosing for 14 days. Urinalysis for laboratory evaluation will be collected after the 24-hour urine PK concludes

and can be collected after administering the morning dose of study drug. Study visits will be on Days 17 (\pm 2 days), 20 (\pm 2 days), 27 (\pm 3 days), 34 (\pm 3 days), and 41 (\pm 3 days). Clinical assessment and physical exam, assessment of AEs and concomitant medications, blood draw, and urine collected will be conducted on Days 17, 27 and 41. As with the Day 7 visit, the evaluations for Day 20 can be conducted locally, with blood and urine collected from the patient's local diagnostic laboratory.

On Day 27 before administration of the morning dose, patients will undergo clinical assessment and physical exam with clinical response calculation, and assessment of AEs and concomitant medications. Patients who are capable of becoming pregnant will have a pregnancy test. If the patient is a Clinical Responder and the drug is well tolerated, then the dosage of 200 mg BID will be extended for 14 more days. The patient will only receive the morning dose on Day 27. Patients will undergo blood draw for research testing and optional collection of PBMCs for storage, urine and fungal culture of the affected site. Samples of blood, urine, saliva, stool (optional), and vaginal secretions (optional) for 24-hour PK analysis will also be conducted, the same as at Day 14.

As with the Days 7 and 20 visits, the visit for Day 34 can be conducted locally, with blood and urine collected from the patient's local diagnostic laboratory.

On Study Day 41 (± 3 days) the following procedures/evaluations will be performed:

- Clinical assessment and physical exam
- Endoscopy with biopsies for EC patients (within 4 weeks of clinical improvement)
- Assessment of AEs and concomitant medications
- Blood draw and urine collection
- Pregnancy testing
- Trough plasma PK collection
- Microbiology (fungal culture of affected sites)
- Optional collection of PBMCs for storage

Study Day 55 (± 3 days) will be the post-treatment End of Study visit for patients who continued 400 mg/day. For this visit, the patient and the investigator have the option of having a phone assessment instead of making a clinical visit. In this

instance the laboratory testing should be performed by a local laboratory and a copy of the results should be sent to the investigator. The following procedures/evaluations will be performed:

- Assessment of AEs
- Blood draw and urine collection

6.5 Dose Escalation to 800 mg/day

If on Day 27 the patient is determined to not be a Clinical Responder but the study drug is well tolerated, then the dosage will be increased to 800 mg/day. These patients will receive only the morning dose (400 mg) on Day 27. The following procedures will be performed:

- Blood draw and urine collection
- Pregnancy testing (result confirmed before administration of dose)
- Collection of 24-hour PK samples: Predose (0-hour timepoint) blood and saliva will be collected, followed by 24-hour PK sampling of blood, urine, saliva, stool (optional), and vaginal secretions (optional)
- Plasma, urine, stool (optional), salivary, and vaginal secretions (optional)
 24-hour timepoint to be collected on Day 28
 Microbiology (fungal culture of affected site)
- Optional collection of PBMCs for storage

Starting on Day 28, patients will be dosed with 800 mg/day (400 mg BID) for 14 days. Prior to dosing, patients will undergo assessment of AEs and concomitant medications. Blood will also be collected for additional laboratory evaluations. Patients will then begin 400-mg BID dosing for 14 days. Urinalysis for laboratory evaluation will be collected after the 24-hour urine PK concludes and can be collected after administering the morning dose of study drug. Study visits will be on Days 30 (± 2 days), 33 (± 2 days), 40 (± 3 days), 47 (± 3 days), 54 (± 3 days) and 68 ((± 3 days). Clinical assessment and physical exam, assessment of AEs and concomitant medications, blood draw, and urine collected will be conducted on Days 30, 40, and 54. As with the Day 7 visit, the evaluations for Days 33 and 47 can be conducted locally, and blood and urine can be collected from the patient's local diagnostic laboratory.

At the Day 40 Study Visit, patients will be assessed for clinical response to study drug. If the patient is determined to not be a clinical responder, the study drug

will be discontinued. Follow-up will occur two weeks later (Day 54 +/- 3 days) and include all of the procedures performed at an Early Termination visit.

If the patient is a clinical responder, (s)he will only receive the morning dose on Day 40. Procedures will be the same as on Day 27.

On Study Day 54 (± 3 days), the following procedures/evaluations will be performed:

- Clinical assessment and physical exam
- Endoscopy with biopsies for EC patients (within 4 weeks of clinical improvement)
- · Assessment of AEs and concomitant medications
- Blood draw and urine collection
- Pregnancy testing
- Trough plasma PK collection
- Microbiology (fungal culture of affected sites)
- Optional collection of PBMCs for storage

Study Day 68 (± 3 days) will be the post-treatment End of Study visit for patients who continued 800 mg/day. For this visit, the patient and the investigator have the option of doing the visit locally instead of making a clinical visit. In this instance the laboratory testing should be performed by a local laboratory and a copy of the results should be sent to the investigator. The following procedures/evaluations will be performed:

- Assessment of AEs
- Blood draw and urine collection

6.6 Extension of Study Drug

Many of the patients expected to enroll into this study have underlying immunodeficiencies that predispose them to chronic mucocutaneous candidiasis, and recurrence is highly likely when the study drug is stopped. Therefore, study participants who are tolerating the study medication and are clinical responders, will be permitted to enroll in a study extension. The extension may be continued from the end of the period of medication administration (i.e. the end of the 2 week period of study medication at the dose that allows efficacy and tolerance of drug) or the participant may have a break of study medication before re-starting the extension period. If there is a break between the initial study drug use and the extension phase, the subjects will be offered alternative antifungals, such as

topical amphotericin swish and spit, to help control the oral pharyngeal candida infection. Breaks in study drug extension will be minimized as much as possible. Any break through infections may be treated by either the Principle Investigator or the subject's Primary Care Provider. In case of recurrence or worsening of the mucocutaneous candida infections while on the extension part of the study drug, despite excellent adherence, that requires new or additional antifungals, the Principal Investigator will stop the study drug.

Study drug will be continued at the minimum dose (100mg BID, 200mg BID, or 400mg BID) meeting clinical responder criteria with good tolerance. The investigator will have the ability to change daily dosage and frequency of study drug based on patient response and tolerability between the range of 200 mg to 800 mg per day.

Extension of study medication will be offered if the following criteria are met:

- Clinical responder status for oral, esophageal or vaginal disease at the end of the 2 week study point at the highest tolerated dose to which they respond (Day 14 for 200 mg, Day 27 for 400 mg, or Day 40 for 800 mg).
- The study participant does not have any of the laboratory criteria meeting the exclusion criteria
 - Alanine Transaminase (ALT), Aspartate Transaminase (AST) and Alkaline phosphatase (ALP) >2.5 times the upper limit of normal (ULN).
 - Total bilirubin level > 2.5 times the ULN
 - Serum creatinine level > 2 times the ULN
 - Absolute neutrophil count less than 500 cells/µL
 - Potassium level <3.5 mmol/L
- Good tolerance of study drug
 - No gastrointestinal toxicity (nausea/vomiting/diarrhea) that is interfering with the ability to perform regular every day activities.
 - Less than two Grade 3 events and/or one Grade 4 event that are possibly, probably, or definitely related to participation in the trial;
 - No SAEs that are possibly, probably or definitely related to the study drug.
- No laboratory abnormalities, intercurrent illness, other medical condition or situation that occurs such that continued participation in the study would not be in the best interest of the subject.

Study medication will be allowed to continue for up to 60 months with the following monitoring:

- Bi-weekly safety laboratories (or more frequently as per PI discretion)
 including CBC/diff, chemistry panels (hepatic, mineral and acute). These
 can be performed at the NIH clinical center or at the home laboratory. (+/4 days)
- Bi-weekly visits to the NIH clinical center (+/- 3 days) for the first 1 month and then the visits can be extended to every 12 weeks (+/- 7 days) unless clinically indicated to be more frequent. At these visits the following study procedures will be performed:
 - Clinical assessment and physical exam
 - Assessment of AEs and concomitant medications
 - Blood draw including CBC/diff, chemistry panels (hepatic, mineral and acute), and urinalysis.
 - Pregnancy testing (except week 2 NIH visit after start of extension phase)
 - Serum and PBMCs may be collected for storage
 - Urine, plasma, stool, saliva and vaginal secretions may be collected and stored
 - Microbiology (fungal culture of affected sites)
 - OMC Picture of affected areas every 8 weeks

If study participants are only seen every 12 weeks, they will be contacted by phone or NIH-approved video conference platform at the 2-week interim point to assess for AEs, concomitant medications, and drug compliance. The laboratory testing can be performed by a local laboratory and a copy of the results should be sent to the investigator.

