4.2 Patient Inclusion Criteria

- Age 18-75 years
- Patients must have a clinical diagnosis of at least one of the following:
 - Persistent OPC for greater than or equal to 5-days documented on at least one occasion by KOH or fungal stain and confirmed by mycological culture to be azole resistant within the previous 6 months and/or intolerance to standard non-intravenous therapies or lack of improvement or worsening of OPC after receipt of appropriately dosed oral azole therapy.
 - EC associated with clinical symptoms of retrosternal pain, odynophagia, and/or pain with swallowing and documented by esophageal biopsy or visualization with culture documenting azole resistance within the previous 6 months and/or intolerance to standard non-intravenous therapies or lack of improvement or worsening of EC after appropriately dosed azole therapy.
 - Persistent VVC for greater than or equal to 5-days as documented by presence of vaginal symptoms and a positive wet mount showing *Candida* structures and confirmed by a vaginal culture positive for *Candida* with azole resistance within the previous 6 months and/or intolerance to standard non-intravenous therapies or lack of improvement or worsening of VVC after receipt of appropriately dosed azole therapy.
- Patient is expected to survive for ≥ 6 months.
- Willing to have samples stored for future research.
- Agree to use highly effective contraception (see below).

Contraception: Because the effects of CAMB on the developing human fetus are unknown, sexually active patients of childbearing potential must agree to Page 22 of 101

use highly effective contraception as outlined below before study entry and for the duration of study participation. Females of childbearing potential must have a negative pregnancy test result before receiving CAMB. During the course of the study, if a patient becomes pregnant or suspects they are pregnant, then they should inform the study staff and their primary care physician immediately. Acceptable forms of contraception are:

- Intrauterine device (IUD) or equivalent.
- Hormonal contraceptives (eg, consistent, timely and continuous use of contraceptive pill, patch, ring, implant, or injection that has reached full efficacy prior to dosing). If the patient uses contraceptive pill, patch, or ring, then a barrier method (eg, male/female condom, cap, or diaphragm plus spermicide) must also be used at the time of potentially reproductive sexual activity.

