4.3 Patient Exclusion Criteria

- Allergy to any AMB product or any component of CAMB (eg, phosphatidylserine)
- Have evidence of systemic fungal infections requiring intravenous antifungal therapy
- Pregnant or nursing women, and women intending to become pregnant during the study period
- Had a concomitant medical condition that could interfere with study drug evaluation or that is a contraindication to the proposed investigational treatment based upon known agent safety profile or toxicities.
- Had any of the following laboratory abnormalities at the screening visit:
 - Alanine Transaminase (ALT), Aspartate Transaminase (AST) and Alkaline phosphatase (ALP) >2.5 times the upper limit of normal (ULN).

- Total bilirubin level > 2.5 times the ULN
- Serum creatinine level > 2 times the ULN
- o Absolute neutrophil count less than 500 cells/µL
- Potassium level <3.5 mmol/L
- Exposure to any investigational agent within 4 weeks prior to Day 0 (Baseline).
- Current or recent history (past 12 months) of drug or alcohol abuse.
- Use of intravenous AMB products within 1-week of start of study drug administration
- Use of non-intravenous AMB products (such as oral AMB swishes)
 within 72 hours prior to start of study drug administration
- Any other condition the investigator believes would interfere with the
 patient's ability to provide informed consent, comply with study
 instructions, or which might confound the interpretation of the study
 results or put the subject at undue risk.

Co-enrollment Guidelines:

Co-enrollment in other trials is restricted, other than enrollment on observational studies. Consideration for co-enrollment in trials evaluating the use of a licensed medication will require the approval of Principal Investigator and Sponsor. Study staff should be notified of co-enrollment as it may require the approval of primary investigator.

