Appendix D Schedule of Procedures/Evaluations – Extension Study

	Extension Entry ¹	Bi-weekly Visits to NIH +/- 3 days) for first month after extension study entry ²	Bi- weekly safety labs (every 2 weeks +/- 4 days) at NIH or local lab ³	Monthly phone calls +/-4 days (at 2 week interim between quarterly NIH visits)	Quarterly visits to NIH (every 12- weeks +/- 7days) ⁴
Informed consent	Х				
Clinical Assessment/Physical Exam	Х	Х	х		Х
Adverse Events and Concomitant Medications, drug compliance	X	X	X	X	X
GYN Exam if applicable	Х	Х			Х
Hematology (CBC/Diff)	Х	Х	Х		Х
Chemistry (Acute, Hepatic, Mineral Panels)	х	Х	х		х
Urinalysis	X	X			X
Pregnancy Testing	X				Х
Microbiology (fungal culture)	X	X			×
Stored Samples (serum & PBMC) ⁵	Х	X			Х
Urine, plasma, stool, saliva and vaginal secretions ⁵	X	X			х
OMC pictures	X				X

All procedures/evaluations for extension study entry are to be conducted during the last treatment visit of the primary study.
 Bi-weekly visits to NIH will be performed in-person at NIH Clinical Center every 2-weeks during first month of the extension.

- 3. Bi-weekly lab draws can be done at the NIH Clinical Center or at the home laboratory. If the visits are conducted at NIH a clinical assessment/physical exam will be performed along with adverse event and concomitant medication collection
- 4. After the first month of the extension, in person visits to the NIH Clinical Center will be quarterly. The 3-month visits will go out to 60 months from the Extension Entry visit. If a patient chooses to terminate the Extension study prior to the 60-month visit, the same monthly procedures/evaluations will be conducted at the Early Termination visit as the Monthly visits.
- 5. These collections are optional.

CAMB for CMC Protocol Version 17.0 May 1,2021

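### When CAMB is restarted for the extension after a break, no new pregnancy test is required: Appendix D puts the entry test before the break

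*Combined protocol and SAP*

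**What the plan says.** Section 6.6 allows the extension to follow directly on treatment, or to begin later: "the participant may have a break of study medication before re-starting the extension period". On length there is only a general aim: "Breaks in study drug extension will be minimized as much as possible".

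Appendix D has an Extension Entry column that includes a pregnancy test. Its footnote 1 fixes when that column is carried out: "All procedures/evaluations for extension study entry are to be conducted during the last treatment visit of the primary study".

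The post-treatment visit comes later. Day 42 "will be the post-treatment End of Study visit for patients who continued 200 mg/day"; Days 55 and 68 serve the same purpose at the higher doses. Sections 6.3 to 6.5 list adverse events, blood and urine at these visits, and no pregnancy test.

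Two rules govern who may be dosed:
- Section 4.2: "Females of childbearing potential must have a negative pregnancy test result before receiving CAMB". No time window is attached.
- Section 6.6 lists the conditions for offering the extension. One reads "The study participant does not have any of the laboratory criteria meeting the exclusion criteria", followed by the liver enzyme, bilirubin, creatinine, neutrophil and potassium limits of 4.3. The separate exclusion in 4.3, "Pregnant or nursing women, and women intending to become pregnant during the study period", is not carried over.

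Once the extension has started, 6.6 lists at NIH visits "Pregnancy testing (except week 2 NIH visit after start of extension phase").

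**The concern.** Footnote 1 suits a participant who continues without interruption: the final on-treatment visit is also the point of entry, and the pregnancy test is current. For a participant who pauses, the same footnote moves the test to before an off-drug interval of unspecified length, and nothing later in the schedule replaces it.

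What is at stake is participant safety. Section 8.1 describes the fetal effects of CAMB as unknown, and 4.4 gives possible teratogenic or abortifacient effects as the reason for excluding pregnant women. A pregnancy that began during the pause would meet no scheduled test before dosing resumed. Section 11.4 takes a pregnant participant off drug, but that protection works only once the pregnancy is known.

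**Working it through.** **1. Reproduce the Appendix E volumes, which show where extension tests fall.** The components are hematology 3 mL, chemistry 4, pregnancy test 4, stored samples 10 and plasma 6.
- Week 2: 3 + 4 + 10 + 6 = 23 mL. This matches the table and contains no pregnancy draw.
- Week 4: 3 + 4 + 4 + 10 + 6 = 27 mL. This matches and contains a pregnancy draw.
- The next 27 mL visit is Week 16. The visits between are 3 + 4 = 7 mL, with no pregnancy draw.

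**2. Look for a test between the start of the break and the first extension dose.** The only core-study visit after treatment ends is Day 42, 55 or 68. Differences in the Appendix C cumulative volumes give 218 − 211 = 7, 308 − 301 = 7 and 398 − 391 = 7 mL, each equal to 3 + 4 (hematology and chemistry). A urine test would not show in blood volumes, so the visit lists carry the weight here. Sections 6.3 to 6.5 name pregnancy testing separately at Days 28, 41 and 54 and do not name it at Days 42, 55 and 68.

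Section 6.6 also lets the extension follow the two-week response visit (Day 14, 27 or 40). Those visits include a pregnancy test too. If a break starts there, that test likewise comes before the break.

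**3. Compare the points at which dosing starts or changes.**

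| Dosing start | Pregnancy test tied to it |
|---|---|
| Day 1, 200 mg/day (6.3) | Yes, same day, listed ahead of the dose |
| Escalation to 400 mg/day (6.4) | Yes, result known before the dose |
| Escalation to 800 mg/day (6.5) | Yes, result known before the dose |
| Extension, straight on (6.6, Appendix D) | Yes, at the final on-treatment visit |
| Extension, after a break (6.6, Appendix D) | None after the break |

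**4. Check whether a general rule fills the last row.** The 4.2 rule has no window, so a core-study test can satisfy it. Section 7.4 says tests are given where the study schedule notes them, and the schedule notes none at restart. The 6.6 entry criteria contain no pregnancy item.

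**5. Find the next scheduled test after restart.**
- Under 6.6 and Appendix E: Week 4, 4 × 7 = 28 days (25 to 31 with the ±3-day window).
- Under the Appendix D grid: the pregnancy row is marked only at entry and at quarterly visits, with nothing in the first-month column. The first quarterly visit in Appendix E is Week 16, 16 × 7 = 112 days (105 to 119 with the ±7-day window).

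The sources conflict, and neither reading places a test before the restart dose.

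**The case against.** The strongest reply is that 4.2 already demands a negative test before CAMB is received, and that the Entry column of Appendix D shows a test was intended at entry. On that view footnote 1 was simply written for the straight-on route, and a careful investigator would test at restart. Contraception is required throughout participation, reminders and compliance checks occur at each visit, participants must report a suspected pregnancy, and 6.6 bars entry when continuing is not in the participant's best interest.

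Much of this stands. A reader might infer that the plan directs an untested restart; it does not. But none of these rules is a test at restart, and footnote 1 as written mistimes the one that the plan schedules.

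A reader might also infer that the wait until Week 4 is itself the fault. The documents do not support that: the straight-on route has the same 28 days, and the extension later accepts 12 × 7 = 84 days between tests. Nor can it be concluded that safety laboratory results would be out of date at restart. The laboratory limits are conditions of the offer, the post-treatment visit includes blood work, and without a stated break length or a single starting visit no age for those results can be derived.

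Finally, reach may be nil. The Protocol Summary says enrollment is closed, 1.1.1 describes participants already in the extension, and 14.1.1 speaks of the final enrolled participant. These suggest that few, if any, restarts remain; they do not establish it.

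**Conclusion.** The point holds as a scheduling gap. On the break route, the plan as written permits CAMB to be restarted on a pregnancy test taken before the break, while every other dosing start in the plan has a test tied to it. The fault is the missing test before the restart dose. The next scheduled test, at day 28 or day 112 depending on which part of the plan is followed, is context, and the disagreement between those sources is a smaller defect to correct at the same time.

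The conclusion rests on reading footnote 1 as covering both routes, since it makes no exception, and on reading 4.2 as having no window, since none is stated. It affects only participants of childbearing potential who take a break. The documents do not show that any such participant exists or still awaits a restart, so no actual fetal exposure can be inferred. The primary endpoint is unaffected. Priority is low.

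**What to change.** Amend Appendix D footnote 1. Keep the present timing for participants who continue without interruption. Add that, for participants of childbearing potential who restart after a break, a negative pregnancy test is confirmed before the first extension dose, using the same condition that 6.4 and 6.5 apply to escalation doses.

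In the same amendment, mark the Week 4 pregnancy test in the first-month column of the Appendix D grid, with Week 2 exempt, so that the grid agrees with 6.6 and Appendix E.

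The cost is one urine test or one 4 mL draw per affected participant and possibly a short delay to restart, during which 6.6 already offers alternative antifungals.
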